6.10 Discontinuation and Withdrawal Criteria

6.10.1 Discontinuation of Treatment

Patients may voluntarily discontinue from treatment for any reason at any time. If a patient decides to discontinue from treatment, the Investigator must make every effort to determine the primary reason for this decision. The reason for discontinuation should be recorded in the patient's chart and on the appropriate eCRF pages.

Patients who discontinue IMP treatment during the Double-Blind Treatment Period should NOT be considered withdrawn from the trial. Every effort will be made to keep patients who discontinue IMP treatment in the trial. They should return for the assessments indicated in Table 3, up to Week 53. A PK sample and an immunogenicity sample should be collected at least 5 weeks after the last dose of IMP.

If the patients fail to return for these assessments for unknown reasons, every effort (e.g., telephone, email, letter) should be made to contact them. Patients who discontinue IMP treatment during the Extension Period should be asked to complete an End-of-Treatment Visit as soon as possible after the last dose of IMP, and a Safety Follow-Up Visit at least 5 weeks after last dose of IMP.

The Investigator should discontinue a patient's IMP treatment if he/she believes that continuation would be detrimental to the patient's well-being or if the patient experiences an intercurrent illness that compromises the patient's ability to fulfil protocol requirements. The Investigator should contact the Medical Monitor before a patient is discontinued from IMP treatment.

IMP treatment must be discontinued under the following circumstances:

- Development of decreased kidney function as defined by $\text{eGFR} < 25 \text{ mL/min/1.73 m}^2$.
- Pregnancy (see [Section 7.6.1.1](#)).
- Any protocol deviation (including prohibited concomitant therapy, see [Section 6.9.3](#)) that results in a significant risk to the patient's safety or that will interfere with the assessment of the efficacy endpoints of this trial, including significant non-compliance with the trial protocol and procedures.

In addition to the general treatment discontinuation criteria, the toxicity-related criteria listed below will also require IMP treatment discontinuation. The final decision to discontinue IMP treatment is up to the judgment of the Investigator.

Hepatic-related Discontinuation Criteria

- ALT or AST levels $> 8 \times$ upper limit of normal.
- ALT or AST levels $> 5 \times$ upper limit of normal for more than 2 weeks.
- Clinically significant and prolonged symptoms of reduced hepatic function, e.g., appearance of chronic fatigue, nausea, vomiting, right upper quadrant pain or tenderness, itchy skin, or swelling of legs and ankles.
- The patient is diagnosed with liver cirrhosis of Child-Pugh class C.
- The patient is diagnosed with hepatic decompensation with European foundation for the study of CLIF-C ACLF score 2 or 3 ([40](#)).

Re-challenge is not recommended when IMP treatment is discontinued due to the above criteria.

For details on follow-up of potential drug-induced liver injury cases, refer to [Section 17.1.1](#), Appendix 1.

Cyst-related Discontinuation Criteria

- Progression of extrahepatic cysts that, in the Investigator's opinion, may prevent the patient from safely participating in the trial.

Cardiac-related Discontinuation Criteria

- $\text{QT/QTcF} \geq 501 \text{ msec}$ or $> 60 \text{ msec}$ increase from baseline (average of triplicate ECG) after repeated triplicate measurement and as confirmed by central ECG reader.
- Torsades de Pointes
- Polymorphic ventricular tachycardia
- Signs/symptoms of serious arrhythmia
- Use of QT-prolonging medication with a known risk of Torsade de Pointes.
- Hypokalemia ($< 3.5 \text{ mmol/L}$) or hypomagnesemia ($< 0.7 \text{ mmol/L}$), or clinically significant hypocalcemia confirmed by repeated testing that is either a new finding or accompanied by vomiting or diarrhea and not corrected by treatment.

For details on QT prolongation management, refer to [Section 17.1.2](#) Appendix 1.

Hyperglycemia-related Discontinuation Criteria

- Patients with hemoglobin A1c $\geq 10\%$ at 3 consecutive visits (including unscheduled visits) despite prior appropriate management.

General Toxicity Discontinuation Criteria

- For ADRs with CTCAE grade 3, treatment should be delayed until the ADR resolves or improves to CTCAE grade ≤ 2 . If the ADR is expected to re-occur upon re-challenge, consider discontinuing IMP permanently. If ADR does not resolve or improve to CTCAE grade ≤ 2 (mild or moderate) within 28 days, IMP must be permanently discontinued.
- For AEs with CTCAE grade ≥ 4 regardless of relatedness to the IMP, treatment will be discontinued until further review.

The events listed above will be reviewed by the DMC while active. Once the DMC is decommissioned, the Sponsor will be responsible for the continued safety monitoring of patients according to the general toxicity discontinuation criteria listed above during the remainder of the Open-Label Extension Period (see [Section 7.7](#) for further details).

6.10.2 Withdrawal from Trial

A patient is free to withdraw his/her consent and discontinue participation in the trial at any time and for any reason. Patients who withdraw consent during a scheduled visit will be asked to complete that visit as the End-of-Treatment Visit. If they withdraw outside of a scheduled visit, they may be asked if they are willing to attend an End-of-Treatment Visit. The reason(s) for discontinuation will be appropriately documented.

All efforts will be made to ensure that all patients are informed of the importance of the clinical trial and collection of data they provide. The Sponsor will continue to retain and use all research results already collected for the trial evaluation. Biological samples that have already been collected may be retained until the trial is completed and reported (or as required by local regulations).

The Investigator will be trained about the importance of patient retention and steps to prevent missing data. The Investigator must maintain a record of all patients who discontinue from the trial before completion; the reason(s) for trial discontinuation will be documented. If a patient chooses to withdraw from the trial, the Investigator should make every effort to obtain and record the reason(s) for withdrawal, if possible, although the patient is not obligated to provide such a reason.

Withdrawn patients will not be replaced.

6.11 Stopping Rules

Based on the extensive safety data available for octreotide over 30 years, the use of CAM2029 in this trial is not expected to be a major concern. However, to ensure the safety of the patients the following stopping criteria will apply for the Double-Blind Treatment Period of the trial:

- More than 2 patients develop an ADR with CTCAE grade 3 or higher in the same preferred term (according to MedDRA).
- Two patients develop any ADR with CTCAE grade 4.
- One patient develops a grade 5 CTCAE.
- Two or more individual patients meet the IMP discontinuation criteria (see [Section 6.10.1](#)).

If all of the above stopping criteria are met or if new data become available that raise concern about the safety of the trial, no more patients will be dosed until the independent DMC has convened, evaluated all safety data from all patients and provided its recommendation as to whether the trial can continue, should remain on hold, or if other actions are warranted.

The DMC will provide their recommendation to the Sponsor, who will make a final decision on how to proceed. When the trial is on hold, no further dosing of any patient will be performed although patients will continue to follow the trial-specific visit schedule. More details about stopping rules and the DMC will be provided in the DMC Charter. See [Section 7.7](#) regarding the function of the DMC and [Section 11.3](#) regarding termination of the trial.

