7 TRIAL ASSESSMENTS AND PROCEDURES

7.1 Trial Procedures and Flow Charts

Trial procedures and their timing for patients during the trial are summarized in [Table 3](#). Protocol waivers or exemptions are not allowed. Immediate safety concerns should be discussed with the Sponsor immediately upon occurrence or awareness to determine if the patient should continue or discontinue trial intervention.

If applicable and if agreed with the Sponsor, visits or specific assessments may be conducted at a patient's home or at a suitable alternative location by mobile qualified and delegated trial personnel. In such cases, the Investigator remains responsible for oversight and protocol procedure adherence. For this purpose, the terms "clinic visit" and "visit to the clinic" in this protocol may also refer to a remote visit.

[figure not shown]

Table 3: Schedule of trial procedures and assessments

	Screening	Double-Blind Treatment Period ^a							
		D1	D8	D29	D85	D141	D169	D267	D365
Procedure/Assessment	W-12 to -1	W1	W2 ^b	W5	W13	W21	W25	W39	W53 ^c
Informed consent	X								
Inclusion/exclusion criteria	X	X ^d							
Demographic data	X								
Medical history including historical liver and kidney ^e volume	X								
Medication/treatment history	X								
Height, BMI	X								
Weight	X	X		X	X		X	X	X
Physical examination	X						X		X
Pregnancy test ^f	X	X ^g			X ^g		X ^g	X ^g	X ^g
Clinical laboratory: hematology, biochemistry, urinalysis, coagulation, thyroid and HbA1c	X ^h	X ^{d,g}		X ^g	X ^g		X ^g	X ^g	X ^g
Serology	X								
Vital signs	X	X ^g			X ⁱ		X ^j	X ^g	X ^g
ECG ^k	X	X ^g			X ⁱ		X ^j	X ^g	X ^g

- a Visit window: ± 1 day for visits with plasma sampling for octreotide measurement and ± 2 days for other visits during the Double-Blind Treatment Period and Extension Period. If the date of a visit does not conform to the schedule, subsequent visits should be planned to maintain the visit schedule relative to the Day 1 visit.
- b Visit may be performed as a phone call.
- c The last dose of IMP in the Double-Blind Treatment Period will be administered in Week 52. The first doses of IMP in the Extension Period will be administered at Week 53 after the last assessments of the Double-Blind Treatment Period have been completed.
- d The Investigator will confirm the patient's eligibility prior randomization on Day 1 based on the data available at the same visit.

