7.7 Data Monitoring Committee

A DMC will be established for this trial. The DMC will include 3 physicians, including 1 hepatologist. Up and until safety data from the last patient in the Double-Blind Treatment Period have been reviewed, the DMC will conduct periodic reviews of safety data and will continuously review all ADRs with CTCAE grade 3 and all AEs with CTCAE grades 4 or 5. The DMC will recommend actions to the Sponsor, as appropriate. The DMC will be informed to what extent the data and analyses provided to them have been quality controlled. Members of the DMC will not be involved in other trial-related tasks.

The DMC will be decommissioned after the safety data from the Double-Blind Treatment Period have been reviewed. The Sponsor will then be responsible for the continued safety monitoring during the remainder of the Open-Label Extension Period.

The DMC procedures are described in the DMC Charter.

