11 CHANGES IN THE CONDUCT OF THE TRIAL

11.1 Protocol Amendments

Any change to this protocol will be documented in a protocol amendment issued by the Sponsor and agreed upon by the Investigator and Sponsor before its implementation. Amendments may be submitted for consideration to the approving IECs/IRBs and regulatory authorities, in accordance with local regulations. Changes to the protocol to eliminate immediate hazard(s) to trial patients may be implemented before IEC/IRB approval/favorable opinion. The Investigator is expected to take any immediate action required for the safety of any patient included in this trial, even if this action represents a deviation from the protocol. In such cases, the Sponsor must be notified of this action, as well as the IEC/IRB and/or regulatory authorities, as required.

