11.3 Premature Trial Termination

Both the Investigator (with regards to his/her participation) and the Sponsor reserve the right to terminate the trial at any time at a given clinical site. The Sponsor also reserves the right to terminate the entire trial or temporarily interrupt enrolment. Should the termination of a given clinical trial site or the whole trial become necessary, the procedures will be agreed upon after consultation between the 2 parties. In terminating the trial, the Sponsor and the Investigator will ensure that adequate consideration is given to protect the patients' best interests. Regulatory authorities and IECs/IRBs will be informed.

Once the 52-week data from the randomized, Double-Blind Treatment Period of the trial are made available, the Sponsor will assess the benefit/risk ratio for the continuation of the Open-Label Extension Period. If the benefit/risk ratio is not positive, the trial will be terminated early.

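### Protocol 6.11 ties the criteria-based dosing hold to all four stopping criteria together, so one grade 5 event or two grade 4 ADRs does not trigger the hold through its own criterion

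*Protocol*

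**What the plan says.** Protocol 6.11 states that "the following stopping criteria will apply for the Double-Blind Treatment Period of the trial" and gives four:

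1. More than 2 patients with an ADR of grade 3 or higher in the same preferred term.
2. Two patients with any grade 4 ADR.
3. "One patient develops a grade 5 CTCAE".
4. Two or more patients who meet the IMP discontinuation criteria of 6.10.1.

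The action sentence reads "If all of the above stopping criteria are met or if new data become available that raise concern about the safety of the trial", and the consequence is that nobody is dosed until the DMC has met, evaluated all safety data and made its recommendation. The section adds: "More details about stopping rules and the DMC will be provided in the DMC Charter".

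Other provisions bear on the same events:

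- 6.10.1 stops treatment, pending review, for a patient with an AE of grade 4 or higher. It also says that the DMC, while active, reviews the events in its list.
- 7.6.1.3 requires SAEs to be reported to the Sponsor within 24 hours.
- Under 7.7 the DMC "will continuously review all ADRs with CTCAE grade 3 and all AEs with CTCAE grades 4 or 5".
- 7.1 says "Immediate safety concerns should be discussed with the Sponsor immediately upon occurrence or awareness", to settle whether the patient continues.
- 11.1: "Changes to the protocol to eliminate immediate hazard(s) to trial patients may be implemented before IEC/IRB approval/favorable opinion".
- 11.3: "The Sponsor also reserves the right to terminate the entire trial or temporarily interrupt enrolment".

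No passage of the Protocol or SAP makes a single criterion sufficient for the hold.

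**The concern.** Patient counts in a stopping rule exist so that a pause does not depend on anyone's judgement at the time. Here the counts are graded by severity (three patients at grade 3 or higher, two at grade 4, one at grade 5), which makes sense if each count acts alone. Joined by 'all', the strictest threshold loses its function: a single death satisfies criterion 3 and nothing follows from that criterion.

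What is at stake is the protection of the other patients while a death or a second grade 4 ADR is being reviewed. Whether their dosing pauses is then left to discretion. The efficacy estimate and its error rates are not involved.

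**Working it through.** The plan gives no figure to reproduce, so the check is mainly one of logic.

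**Truth table.** Four criteria, each met or not, give 2^4 = 16 patterns. Under 'all', 1 of 16 triggers the criteria-based hold. Under 'any', 15 of 16 would.

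**Single cases under the rule as written.**

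- One grade 5 event alone: criterion 3 is met; criteria 1, 2 and 4 are not. No criteria-based hold.
- Two grade 4 ADRs: criterion 2 is met, and so is criterion 4, through the grade 4 or higher rule in 6.10.1. Criteria 1 and 3 are not necessarily met, and 3 cannot be without a grade 5 event. No criteria-based hold.
- Any number of grade 3 or 4 ADRs without a grade 5 event: criterion 3 is unmet, so the numeric hold cannot fire.

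**Smallest triggering set.** Criterion 1 alone needs 3 patients, so 3 is a lower bound. It is attainable: three patients with ADRs of grade 3 or higher in one preferred term, two of them with grade 4 ADRs and one with a grade 5 event. The stated thresholds are 1 patient for grade 5 and 2 for grade 4.

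**Internal evidence on intent.** Under 'all', criterion 4 adds nothing, because two grade 4 ADRs already meet it. It has a function only if criteria can act separately. This suggests that 'any' was meant, but it is an inference.

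**Illustrative probabilities.** The documents give no event rates, so all rates here are assumptions: n = 69, patients independent, and deaths independent of ADRs. Low, mid and high cases:

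| Quantity | Low | Mid | High |
|---|---|---|---|
| Assumed death rate; grade 4 ADR rate (each) | 0.25% | 0.5% | 1% |
| Assumed grade 3 or higher ADR rate, in each of ten terms | 0.5% | 1% | 2% |
| Criterion 3: 1 − (1 − p)^69 | 0.16 | 0.29 | 0.50 |
| Criterion 2: P(X ≥ 2) | 0.01 | 0.05 | 0.15 |
| Criterion 1: 1 − (1 − P(X ≥ 3))^10 | 0.05 | 0.28 | 0.83 |
| All four met, given a death | about 0.2% | about 2% | about 14% |
| Any of criteria 1 to 3 | 0.21 | 0.51 | about 0.92 |

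The last two rows treat grade 4 ADRs as a subset of grade 3 or higher ADRs (simulation of 200,000 trials). Criterion 4, P(X ≥ 2) at assumed rates of 2%, 5% and 10% per patient, is 0.40, 0.87 and 0.99.

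**Timing.** Protocol 4.3 plans the last patient's first visit for Q4 2023. Assume 31-Dec-2023 and the full 12 weeks of screening: Day 1 is 24-Mar-2024. The last double-blind dose is in Week 52 (Table 3, footnote c), 51 weeks later: 16-Mar-2025. That is 46 days after the protocol version of 29-Jan-2025.

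**The case against.** The strongest reply is that the criteria are not the only route to a hold. The new-data branch of the same sentence is open-ended, and once it is judged met the hold is mandatory. A death would reach the Sponsor within 24 hours and the DMC through its continuous review, so prompt notice and independent review are assured. The Charter could state that a death, or any single criterion, counts as such new data; that would be consistent with the protocol text, so the gap may not exist in operation.

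Most of this stands. A reader might infer that a death would go unreviewed, or that dosing could not be paused until all four criteria were met. The documents do not support either inference. Nor do they support saying that the Charter could not cure the wording.

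What remains is narrower. The route through new data depends on a judgement of concern that the Protocol does not define. 7.7 provides for review and recommendation, without a pause in the meantime. 7.1 and the grade 4 or higher rule in 6.10.1 concern the affected patient. 11.1 is a discretionary urgent measure, and 11.3 speaks of terminating the trial or interrupting enrolment, not of pausing dosing.

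**Conclusion.** The wording is defective and should be corrected. As written, the numeric hold needs all four criteria, at least 3 affected patients and at least one grade 5 event, against stated thresholds of 1 and 2 patients for the two most severe grades. This follows from the text and needs no assumed rates, apart from taking a grade 4 or 5 patient to meet the 6.10.1 discontinuation criteria.

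The practical consequence is less certain than the wording, because it depends on a Charter that is not available. The trip probabilities are illustrative only; they range too widely to rank the options.

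A reader might also infer a threat to the trial's efficacy conclusion. There is none: the primary analysis does not use this rule. Urgency is limited by scope (the Double-Blind Treatment Period only) and, if enrolment kept to plan, by the short time left for dosing after the current protocol version.

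**What to change.** In 6.11, replace the opening condition of the action sentence with: 'If any one of the first three stopping criteria is met'. Keep the new-data branch and the consequence unchanged.

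The sponsor should decide explicitly whether criterion 4 alone leads to a hold or to a DMC review. It should not simply be swept into 'any', because 6.10.1 includes non-toxicity reasons such as pregnancy, and two discontinuations among 69 patients may be common (0.40 to 0.99 under the rates assumed above).

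Align the DMC Charter, and have the DMC confirm in writing which reading it has applied so far. If double-blind dosing has already ended, that confirmation and a statement in the clinical trial report are enough.

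**Cost.** A short protocol amendment, a Charter edit and one written confirmation. The real downside is more temporary holds, including after an unrelated death, since criterion 3 does not require relatedness. Missed doses are not made up (6.2.2), so an assumed 4-week hold would cost a patient on treatment up to 4 of 52 weekly injections (4/52 = 7.7%).

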6.12 Lost to Follow-Up

For patients whose status is unclear because they fail to appear for trial visits without stating an intention to withdraw consent, the Investigator should contact the patient and document the steps taken to do so in the source documents, e.g., dates of telephone calls, registered letters, etc.

A patient should not be considered lost to follow-up until due diligence (3 documented telephone contacts and a registered letter) has been completed. Patients who are lost to follow-up should be recorded as such in the eCRF.

7 TRIAL ASSESSMENTS AND PROCEDURES

7.1 Trial Procedures and Flow Charts

Trial procedures and their timing for patients during the trial are summarized in [Table 3](#). Protocol waivers or exemptions are not allowed. Immediate safety concerns should be discussed with the Sponsor immediately upon occurrence or awareness to determine if the patient should continue or discontinue trial intervention.

If applicable and if agreed with the Sponsor, visits or specific assessments may be conducted at a patient's home or at a suitable alternative location by mobile qualified and delegated trial personnel. In such cases, the Investigator remains responsible for oversight and protocol procedure adherence. For this purpose, the terms "clinic visit" and "visit to the clinic" in this protocol may also refer to a remote visit.

[figure not shown]

Table 3: Schedule of trial procedures and assessments

	Screening	Double-Blind Treatment Period ^a							
		D1	D8	D29	D85	D141	D169	D267	D365
Procedure/Assessment	W-12 to -1	W1	W2 ^b	W5	W13	W21	W25	W39	W53 ^c
Informed consent	X								
Inclusion/exclusion criteria	X	X ^d							
Demographic data	X								
Medical history including historical liver and kidney ^e volume	X								
Medication/treatment history	X								
Height, BMI	X								
Weight	X	X		X	X		X	X	X
Physical examination	X						X		X
Pregnancy test ^f	X	X ^g			X ^g		X ^g	X ^g	X ^g
Clinical laboratory: hematology, biochemistry, urinalysis, coagulation, thyroid and HbA1c	X ^h	X ^{d,g}		X ^g	X ^g		X ^g	X ^g	X ^g
Serology	X								
Vital signs	X	X ^g			X ⁱ		X ^j	X ^g	X ^g
ECG ^k	X	X ^g			X ⁱ		X ^j	X ^g	X ^g

- a Visit window: ± 1 day for visits with plasma sampling for octreotide measurement and ± 2 days for other visits during the Double-Blind Treatment Period and Extension Period. If the date of a visit does not conform to the schedule, subsequent visits should be planned to maintain the visit schedule relative to the Day 1 visit.
- b Visit may be performed as a phone call.
- c The last dose of IMP in the Double-Blind Treatment Period will be administered in Week 52. The first doses of IMP in the Extension Period will be administered at Week 53 after the last assessments of the Double-Blind Treatment Period have been completed.
- d The Investigator will confirm the patient's eligibility prior randomization on Day 1 based on the data available at the same visit.
- e Historical kidney volume will be collected, if available in medical records, in patients with confirmed ADPKD.
- f Serum pregnancy test at screening; urine pregnancy test at other visits.
- g Pre-dose.
- h Performed within 4 weeks prior to the Day 1 Visit.
- i Pre-dose and 24 ± 4 hours after dose.
- j Pre-dose and 24 ± 14 hours after dose.
- k Triplicate 12-lead ECG will be performed.

	Screening	Double-Blind Treatment Period ^a							
		D1	D8	D29	D85	D141	D169	D267	D365
Procedure/Assessment	W-12 to -1	W1	W2 ^b	W5	W13	W21	W25	W39	W53 ^c
Gallbladder examination ^l	X ^{m,n}								
MRI of liver and kidney volume and total liver cyst volume	X ^{h,o}				X ^p		X ^p		X ^p
Administration of IMP ^q		X	X	X	X	X	X	X	X
eGFR sampling (creatinine, cystatin C)	X	X ^g			X ^g		X ^g		X ^g
Plasma samples for octreotide measurement		X ^g			X ^r		X ^j	X ^g	X ^g
Immunogenicity		X ^g			X ^g		X ^g		X ^g
PLD-S	X	X ^g			X ^g	X ^g	X ^g	X ^g	X ^g
PLD-I	X	X ^g			X ^g	X ^g	X ^g	X ^g	X ^g
PGI-S	X	X ^g			X ^g	X ^g	X ^g	X ^g	X ^g
PGI-C					X ^g	X ^g	X ^g	X ^g	X ^g
SF-36		X ^g					X ^g		X ^g
PLD-Q		X ^g					X ^g		X ^g

- ^l Gallbladder imaging may be repeated during the trial if symptoms of cholelithiasis appear (ultrasound is first choice).
- ^m Historical gallbladder imaging assessments performed within 4 months before Day 1 Visit, may be used as baseline measurement. If such a gallbladder ultrasound or MRI is available and includes satisfactory information on presence of gallstones, gallbladder sludge or other findings, the screening gallbladder ultrasound does not need to be performed.
- ⁿ If the MRI of the liver and kidneys performed at screening, Week 77, Week 125 and Week 173/End-of-Treatment include satisfactory images of the gallbladder, these scans may also be used for the safety assessment by the Investigator.
- ^o The eligibility htTLV value will be calculated according to local clinical practice either using the MRI at screening or based on available historical imaging, as long as that the latter fulfils the imaging and schedule requirements of the trial (see footnote ^h and Section 7.3.1).
- ^p Visit window ± 3 days.
- ^q The IMP will be administered every week during the Double-Blind Treatment Period (and every 2 weeks during the Extension Period) aligned from Day 1 (± 2 days) by self- or partner-administration or by the trial personnel. For home administrations the Investigator or designated personnel will dispense an appropriate number of IMP packages. Home administration of the IMP may be performed at Weeks 2-4, 6-12, 14-20, 22-24, 26-38, 40-52, 54-56, 58-64, 66-76, 78-88, 90-100, 102-124, 126-148, 150-160 and 162-172. For patients who are not self- or partner-injecting at home, visits for IMP administration will be performed during the Double-Blind Treatment Period. At visit days, assessments should be performed before dosing.
- ^r Pre-dose and 2 ± 1 , 5 ± 1 , 24 ± 4 , 96 ± 24 and 168 ± 24 hours after dose.
- ^s
- ^t

	Screening	Double-Blind Treatment Period ^a							
		D1	D8	D29	D85	D141	D169	D267	D365
Procedure/Assessment	W-12 to -1	W1	W2 ^b	W5	W13	W21	W25	W39	W53 ^c
									
CGI-S		X ^g			X ^g	X ^{g,v}	X ^g		X ^g
Concomitant medication	X	X	X	X	X	X	X	X	X
AEs	X	X	X	X	X	X	X	X	X

u

^v In those cases where the at-home visit is needed, a video-call will be set up to allow CGI-S assessment by the Investigator.

Confidential

	Extension Period ^a											Safety FU Period ^b
	D393	D449	D533	D617	D701	D785	D869	D953	D1037	D1121	D1205	D1265
Procedure/Assessment	W57	W65	W77	W89	W101	W113 ^b	W125	W137 ^b	W149	W161 ^b	W173 EOT	W181 Safety FU
Informed consent												
Inclusion/exclusion criteria												
Demographic data												
Medical history including historical liver and kidney ^e volume												
Medication/treatment history												
Height, BMI												
Weight	X	X	X	X	X		X		X		X	
Physical examination			X		X		X		X		X	
Pregnancy test ^f	X ^g	X ^g	X ^g	X ^g	X ^g		X ^g		X ^g		X	
Clinical laboratory: hematology, biochemistry, urinalysis, coagulation, thyroid and HbA1c	X ^g	X ^g	X ^g	X ^g	X ^g		X ^g		X ^g		X	
Serology												
Vital signs		X ^j	X ^g	X ^g	X ^g		X ^g		X ^g		X	
ECG ^k		X ^j	X ^g	X ^g	X ^g		X ^g		X ^g		X	
Gallbladder examination ^l			X ⁿ				X ⁿ				X ⁿ	
MRI of liver and kidney volume and total liver cyst volume			X ^{n,p}				X ^{n,p}				X ^{n,p}	
Administration of IMP ^q	X	X	X	X	X	X	X	X	X	X		
eGFR sampling (creatinine, cystatin C)		X ^g	X ^g		X ^g		X ^g		X ^g		X	
Plasma samples for octreotide measurement		X ^j									X	X
Immunogenicity		X ^g	X ^g		X ^g		X ^g		X ^g		X	X
PLD-S			X ^g		X ^g		X ^g		X ^g		X	
PLD-I			X ^g		X ^g		X ^g		X ^g		X	
PGI-S			X ^g		X ^g		X ^g		X ^g		X	
PGI-C			X ^g		X ^g		X ^g		X ^g		X	
SF-36			X ^g		X ^g		X ^g		X ^g		X	

	Extension Period ^a											Safety FU Period ^b
	D393	D449	D533	D617	D701	D785	D869	D953	D1037	D1121	D1205	D1265
Procedure/Assessment	W57	W65	W77	W89	W101	W113 ^b	W125	W137 ^b	W149	W161 ^b	W173 EOT	W181 Safety FU
PLD-Q			X ^g		X ^g		X ^g		X ^g		X	
[REDACTED]	[REDACTED]											
[REDACTED]												
[REDACTED]												
[REDACTED]												
[REDACTED]												
[REDACTED]												
[REDACTED]												
CGI-S			X		X		X		X		X	
Concomitant medication	X	X	X	X	X	X	X	X	X	X	X	X
AEs	X	X	X	X	X	X	X	X	X	X	X	X ^w

AE: adverse event; [REDACTED]; BMI: body mass index; [REDACTED]; CGI-S: Clinical Global Impression of Severity; D: Day; ECG: electrocardiogram; eGFR: estimated glomerular filtration rate; EOT: End-of-Treatment; FU: Follow-Up; HbA1c: hemoglobin A1c; [REDACTED]; IMP: investigational medicinal product; MRI: magnetic resonance imaging; PGI-C: Patient Global Impression of Change; PGI-S: Patient Global Impression of Severity; PLD-I: Polycystic Liver Disease Impact; PLD-Q: Polycystic Liver Disease Questionnaire; PLD-S: Polycystic Liver Disease Symptoms; [REDACTED]; SAE: serious adverse event; [REDACTED]; W: Week.

^w For new SAEs considered related to IMP and follow-up of AEs not resolved at Week 173.

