4.1.4 Safety Follow-Up Period

A Safety Follow-Up Visit will be performed 8 weeks after the Week 173/End-of-Treatment Visit to assess PK and immunogenicity, and to collect information regarding any AEs ongoing at Week 173 and any new SAEs considered related to the IMP.

4.2 Rationale of Overall Trial Design, Endpoints, Trial Population, and Choice of Control Groups and Dose

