7.4 Pharmacokinetic Assessment

7.4.1 Blood Collection and Handling

Blood samples for evaluation of plasma concentrations of octreotide will be collected from all patients at the time points indicated in Table 3. In exceptional cases where a blood sample for plasma octreotide concentration assessments cannot be taken, e.g., for logistic or patient personal reasons, this may be considered acceptable after agreement with the Sponsor.

Blood samples will be taken by either direct venipuncture or indwelling cannula inserted in a forearm vein.

The date and exact time of dosing, as well as the date and exact time of blood sampling, must be recorded on the eCRF. Detailed instructions for the collection, handling, and shipment of blood samples will be provided separately.

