7.6.4 Immunogenicity Assessments

Blood samples for immunogenicity assessment of anti-drug antibodies will be taken according to [Table 3](#). Detailed method descriptions of the immunogenicity assays will be provided separately.

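### Table 3 lets the Week 181 Safety Follow-Up Visit be a phone call, although that visit carries the last scheduled octreotide and antibody samples and exists to collect them

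*Protocol*

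**What the plan says.** In Protocol Section 7.1, footnote b to Table 3 reads "Visit may be performed as a phone call". In the extension half of the table the footnote is on the Week 113, 137 and 161 columns and also on the last header, printed as "Safety FU Period ^b". That header covers one visit, Week 181. Its column has an X in the row "Plasma samples for octreotide measurement" and another in the row "Immunogenicity".

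Section 4.1.4 gives the reason for the visit: "A Safety Follow-Up Visit will be performed 8 weeks after the Week 173/End-of-Treatment Visit to assess PK and immunogenicity". It also collects follow-up on adverse events.

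Both samples need blood. Section 7.4.1 says of octreotide sampling: "Blood samples will be taken by either direct venipuncture or indwelling cannula inserted in a forearm vein". Section 7.6.4 says: "Blood samples for immunogenicity assessment of anti-drug antibodies will be taken according to" Table 3.

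Section 7.4.1 tolerates a missing octreotide sample only exceptionally and with the sponsor's agreement. Section 7.1 allows assessments at home by mobile trial staff if the sponsor agrees. Neither provision is linked to footnote b.

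**The concern.** The visit can be done in a form that cannot deliver the samples it is meant to collect. The other visits with footnote b (Weeks 2, 113, 137 and 161) show no blood sampling in the legible rows of Table 3. They carry IMP administration, concomitant medication and adverse events, which a call can handle. Week 181 is the only visit open to a phone call that also has a blood draw.

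At stake is the off-drug PK and anti-drug-antibody information at the end of long-term treatment. The protocol treats immunogenicity as a safety question (Sections 2.2.2 and 4.2.2). Patients who stop IMP in the double-blind period have an explicit rule requiring a PK and an immunogenicity sample at least 5 weeks after the last dose (Sections 4.1.2 and 6.10.1). Extension completers have no such rule beyond the Week 181 visit. Extension discontinuers are asked for a Safety Follow-Up Visit at least 5 weeks after the last dose, which is the same visit type. No later visit exists at which a missed sample could be taken.

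**Working it through.** The plan states no figure to reproduce here. The check is a cross-reading of the schedule plus arithmetic on timing.

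**Inputs**
- Week 173/End-of-Treatment is D1205 and the Safety Follow-Up is printed as D1265 (Table 3).
- The Safety Follow-Up is 8 weeks after Week 173 (Section 4.1.4).
- The last extension dose is at Week 172 (Section 4.1.3). Dosing every 2 weeks from Week 53 falls on odd-numbered weeks, so strict spacing would put the last dose before Week 173 at Week 171. Both are carried below, and the protocol should reconcile them.
- The half-life is 10.6 days and 5 half-lives are 53 days (SAP Sections 5.10.1 and 5.8.1).
- Assumption: first-order decline, so the share remaining is 0.5^(days/10.6).

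**Visit days**, from day = 7 × (week − 1) + 1:
- Week 171 = 7 × 170 + 1 = D1191
- Week 172 = 7 × 171 + 1 = D1198
- Week 173 = 7 × 172 + 1 = D1205, as printed
- Week 181 = 7 × 180 + 1 = D1261, and also 1205 + 56 = 1261

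The other extension columns fit this formula. The printed D1265 is 60 days after D1205, 4 days more than 8 weeks.

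**Drug remaining at each sample**

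| Last dose | Sample | Days since dose | Half-lives | Remaining |
|---|---|---|---|---|
| Week 172 | Week 173 | 1205 − 1198 = 7 | 0.66 | 63.3% |
| Week 171 | Week 173 | 1205 − 1191 = 14 | 1.32 | 40.0% |
| Week 172 | Week 181 (D1261) | 1261 − 1198 = 63 | 5.94 | 1.6% |
| Week 171 | Week 181 (D1261) | 1261 − 1191 = 70 | 6.60 | 1.0% |

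Using D1265 instead gives 67 or 74 days and 1.3% or 0.8%, so the day label does not alter the conclusion.

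**Reading across.** The extension antibody samples at Weeks 65, 77, 101, 125 and 149 are taken during dosing. Week 173 is 7 to 14 days after the last dose, inside the 53-day window. Only Week 181 lies outside it. For a completer, the number of scheduled post-exposure samples beyond 5 half-lives is one if blood is drawn at Week 181 and none if the visit is only a call.

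For an extension discontinuer, the earliest permitted Safety Follow-Up is 35 days after the last dose: 35/10.6 = 3.3 half-lives, about 10% remaining. The statement about 5 half-lives therefore applies to completers. Discontinuers depend on the same visit type for their late sample, but it may be less fully washed out.

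**The case against.** The strongest reply is that footnote b governs only the form of contact. It does not delete the X marks. Section 7.1 rules out waivers, Section 7.6.4 ties antibody sampling to Table 3, and Section 7.4.1 restricts missed octreotide samples. A phone call for adverse events combined with a home blood draw would satisfy every provision. This stands in part: a reader might infer that a site which simply telephones has fully complied, and the documents do not support that. But they also do not say that the draw is still required when the call option is used, so the schedule contradicts the stated purpose of the visit.

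Other stronger readings also fail:
- *Week 181 holds the only post-treatment samples.* Week 173 has both samples, taken after the last dose.
- *It is the only drug-free antibody sample.* Day 1 pre-dose is drug-free, and so are the placebo arm's double-blind samples. What holds is that it is the only post-exposure sample beyond 5 half-lives for completers.
- *D1265 breaches the visit window.* Footnote a's windows are stated for the Double-Blind and Extension Periods, not for Safety Follow-Up.
- *The planning drop-out caps the number exposed at about 58 (69 × 0.85 = 58.65).* The 15% is a sample-size assumption, not a bound, and extension entry has further conditions.

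Two cautions remain. How much a drug-free antibody sample adds depends on the assay's drug tolerance, and Section 7.6.4 leaves the assay details to separate documents. The point also rests on one superscript read from extracted text. It sits on the period header, whereas elsewhere footnote b is on the week labels.

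**Conclusion.** The point holds as an internal inconsistency. Table 3 permits a phone call for a visit that Section 4.1.4 defines by its PK and immunogenicity assessments, and no text closes the gap. The consequence for an extension completer whose visit is only a call is the loss of the one scheduled post-exposure PK and antibody time point beyond 5 half-lives, at 63 to 70 days and about 1–2% of drug remaining. Week 173, at 7 to 14 days and about 40–63%, does not replace it.

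A reader might infer that these data will be lost for every completer. The footnote is permissive and a home draw is available, so loss is possible but not certain, and the documents give no basis for its frequency. The effect is confined to late PK and immunogenicity data. The Week 53 primary and key secondary analyses are untouched, and this SAP covers only the double-blind period. The percentages assume first-order decline with the SAP half-life and a last dose at Week 171 or 172. The D1265/D1261 mismatch is real but clerical.

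**What to change.** First check the superscript on the Safety Follow-Up header against the PDF. If it is confirmed, either remove footnote b from that column, or limit it to the adverse-event and concomitant-medication rows and add a sentence that the Week 181 plasma and immunogenicity samples must still be drawn, at site or by the home-visit route already in Section 7.1. Either wording brings Table 3 into line with Sections 4.1.4, 7.4.1 and 7.6.4.

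In the same amendment, reconcile the printed D1265 with Week 181 = D1261.

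The cost is one footnote and one day number. The downside is that a call alone can no longer replace the visit, so some patients will need a site attendance or a home draw.
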